9 INVESTIGATIONAL PLAN

9.1 Overall Study Design and Plan

Study 111-202 is a pediatric, Phase 2, open-label dose-escalation study of approximately 36 subjects with a clinical diagnosis of ACH. Subjects who are 5 to 14 years old inclusive, with documented ACH confirmed by genetic testing, have at least a 6-month period of pretreatment growth assessment in Study 111-901 immediately before study entry, and who meet the study eligibility criteria will participate. BMN 111 will be administered daily for 6 months, provided none of the protocol-defined stopping or safety criteria, defined below, are met. On days of scheduled clinic visits, BMN 111 administration will be performed in the clinic relative to the scheduled assessments and procedures defined in the 111-202 Schedule of Events ([Table 9.1.1](#)).

Comprehensive outpatient safety monitoring will be conducted for all subjects over the course of the first 10 days after the first dose of study drug is received, followed by close monitoring throughout the duration of the study. The comprehensive safety monitoring includes a minimum of 8 hours post-dose observation on the first two days of dosing and at least 4 hours post dose observation on study Days 3 and 4. Subjects may be observed for a longer duration and/or additional visits may be added for further safety assessment on Days 5-9 at the discretion of the Investigator in consultation with the BioMarin Medical Monitor. A visit on Day 10 concludes the comprehensive outpatient safety-monitoring period. Vital signs will be monitored frequently during the initial period of Days 1-10, including approximately every 10-20 minutes for the first 2 hours post dose on visit days. Additional safety assessments during this period are ECG, physical exams, AE assessment, and clinical labs ([Table 9.1.1](#)).

A maximum of five children from one gender may be enrolled in each cohort if the total size of the cohort is eight or nine subjects; a maximum of six children from one gender can be enrolled in each cohort if the size of the cohort is 10 subjects.

BMN 111 will be administered as a morning dose in one of the following daily dosing regimens:

- Cohort 1 (n=8): daily morning dose of 2.5 µg/kg BMN 111
- Cohort 2 (n=8): daily morning dose of up to 7.5 µg/kg BMN 111
- Cohort 3 (n=8-10): daily morning dose of up to 15.0 µg/kg BMN 111
- Cohort 4 (n=8-10): daily morning dose of 30.0 µg/kg BMN 111

It is generally expected that after subjects are tolerating the drug well and specified criteria have been met, caregivers will begin administering study drug. In the initial phase, on weeks when caregivers/subjects will not see either a home healthcare professional or a study staff member, a phone call by the study staff member to the caregiver/subject will be required. During the call, study staff will ask the caregiver about correct administration procedures, assess adverse events (AEs), record concomitant medications, and answer questions. During the optional, open-label extension phase, the call frequency will change to every 2 weeks (± 3 days) for the first 6 months of the extension phase and monthly (± 5 days) thereafter. A follow-up phone call will take place 7-10 days after dose adjustment visits.

Dose Escalation Plan during the Initial 6 Months of the Study

For each cohort, two sentinel subjects will be enrolled and monitored. A DMC review will occur after both sentinel subjects reach Day 10; if stopping criteria are not met, and after review and approval by the DMC, the remainder of the cohort may then be enrolled.

Subjects will remain on a fixed daily dose throughout the initial 6-month treatment period. Subjects in each cohort continue to receive daily dosing (Cohort 1, 2.5 $\mu\text{g}/\text{kg}$; Cohort 2, up to 7.5 $\mu\text{g}/\text{kg}$, Cohort 3, up to 15 $\mu\text{g}/\text{kg}$, and Cohort 4, 30.0 $\mu\text{g}/\text{kg}$) for 6 months unless stopping criteria are met. If stopping criteria are not met after all 8-10 subjects in a cohort have completed their first 10 days of cohort dosing, and after DMC review and approval, the subsequent cohort may be open to enrollment.

Optional, Open-label Extension Phase of the Study

In the open-label, optional extension phase, the long-term safety, tolerability, and effects of BMN 111 on growth will be evaluated in children with ACH who have completed an initial 6 months of treatment with BMN 111. At the Day 183/6-month visit, subjects who elect to continue participating in the optional open-label extension phase will be consented for the extension phase. These subjects will receive study drug on Day 184 of the initial phase, which also marks the beginning of the extension phase. Drug treatment will continue without interruption. Subjects who decline to participate in the extension phase will return at Day 208 for the Safety Follow-Up visit and exit the study.

In the 18-month optional, open-label extension phase, subjects within each cohort will either remain on the same stable dose that they have been receiving during the initial 6 months of treatment, or the dose for all subjects in the cohort (except cohort 4) may be increased based on the following rules:

(1) Initial dose was determined to exhibit suboptimal efficacy on the basis of growth measurements after at least 6 months of treatment based on the review of the data for all subjects in the cohort.

(2) Initial dose, and other doses higher than the initial dose, but lower than the dose to which the cohort is being increased were generally well tolerated for at least 6 month based on review of data for all subjects in the cohort.

(3) The dose to which the subjects in the cohort are being escalated has been previously shown to be well tolerated for at least 10 days of comprehensive outpatient safety monitoring as described in Section 9.1, based on DMC review of the data for all subjects in the cohort previously assigned to the considered dose.

During the optional, open-label extension phase, visits will take place at 2- to 3-month intervals. The site will call the caregiver/subject between the visits every two weeks for the first 6 months and every month for the remainder of the study.

DMC data review will occur approximately every 4 months during the optional, open-label extension phase.

Subjects who participate in the open-label extension phase of study 111-202 will have the option to enroll in the long-term extension study 111-205 at the Month 24/Study Completion Visit. Month 24 assessments will serve as Baseline/screening assessments for entry to study 111-205.

Criteria for Dose Adjustment Visits

The timing of dose adjustments and follow-up visits after adjustment is contingent upon the time at which the dose adjustment was recommended. One of two scenarios will apply:

- Scenario 1: Recommendation to adjust the dose is made when the next scheduled visit is ≤ 4 weeks away from the date that the dose change is communicated to sites. Dose adjustment will be done at the next scheduled visit.
- Scenario 2: Recommendation to adjust the dose is made when the next scheduled visit is > 4 weeks away from the date that the dose change is communicated to sites. An unscheduled dose adjustment visit will be done within 4 weeks.

[figure not shown]
In both cases, a follow-up visit 4 weeks (± 2 weeks) is required after the dose adjustment. The dose adjustment follow-up visit will be scheduled 4 weeks after the dose adjustment visit UNLESS a regularly scheduled visit occurs within the ± 2 -week visit window, in which case a separate follow-up visit will not be required.

Please refer to [Table 9.1.3](#) for a list of assessments associated with Dose Adjustment and Follow-up Visits.

Assessments

For a discussion of efficacy assessments, see [Section 9.10.2](#); exploratory efficacy assessments, [Section 9.10.3](#); safety assessments, [Section 9.10.4](#); and PK/PD variables, [Sections 9.10.2.1](#) and [9.10.3.1](#). The 111-202 study design is presented in [Figure 9.1.1](#).

Figure 9.1.1: 111-202 Study Design

- ▲ Study start
- ▮ 2 sentinel subjects enroll and receive 10 days dosing.
- ▮ 2 sentinel subjects complete 10 days dosing, DMC reviews safety and available PK data; if stopping criteria not met, remaining 6 subjects for that cohort enroll and receive 10 days of dosing.
- ▮ DMC reviews safety and available PK data for all 8 subjects after 10 days of dosing. If stopping criteria not met, next higher dose cohort opens. At the same time, subjects in that cohort will continue to receive daily dosing for 24 months unless stopping criteria are met.
- ↻ 3-month rolling DMC safety and available PK data reviews during primary phase; 6-month reviews during extension phase.

A summary of events and assessments are provided by visit in [Table 9.1.1](#).

BOMARIN[®]	BMN 111-202 Amendment 4	Page 39
----------------------------	-------------------------	---------

Table 9.1.1: Schedule of Events for 6-Month Initial Phase of the Study

Procedure ^a	Screening Day -30 to Day -1	Day 1	Day 2	Day 3	Day 4	Day 10 ± 1 Day	Day 15 ± 1 Day	Day 22 ± 1 Day	Day 29 ± 1 Day	Day 43 ± 7 Days	Day 85 ± 7 Days	Day 127 ± 7 Days	Day 183 ± 7 Days M6	Safety Follow-up Day 208 ± 7 Days	Early Term
Informed consent	X												X		
Medical history ^b	X														
Parental height ^c	X ^c														
Genetic testing (if needed) ^d	X														
Physical examination ^e	X	X	X	X	X	X	X	X	X	X	X	X	X	X	X
Tanner Stage of Pubertal Development	X												X		X
Pregnancy test ^e	X									X	X	X	X	X	X
Vital signs ^f	X	X	X	X	X	X	X	X	X	X	X	X	X	X	X
Anthropometric measurements ^g	X									X	X	X	X		X ^g
Weight	X	X	X	X	X	X	X	X	X	X	X	X	X		X
Elbow joint range of motion ^h	X									X	X	X	X	X	X
Baseline hip assessment, including AP x-ray of pelvis ⁱ	X														
Hip monitoring (refer to guidance) ^j													X		X
Sleep apnea assessments ^k	X										X		X		X
ECG	X					X			X		X		X	X	X
ECHO	X												X		
Clinical labs	X	X			X	X	X		X	X	X	X	X	X	X

BOMARIN[®]	BMN 111-202 Amendment 4	Page 40
----------------------------	-------------------------	---------

Procedure ^a	Screening Day -30 to Day -1	Day 1	Day 2	Day 3	Day 4	Day 10 ± 1 Day	Day 15 ± 1 Day	Day 22 ±1 Day	Day 29 ±1 Day	Day 43 ±7 Days	Day 85 ± 7 Days	Day 127 ±7 Days	Day 183±7 Days M6	Safety Follow-up Day 208 ±7 Days	Early Term
(hematology, chemistry, and urinalysis) ^l															
Urine chemistry ^m	X	X				X	X	X	X	X	X	X	X	X	X
Thyroid function tests	X												X		
Serum glucose levels	X												X		
Vitamin D	X												X		X
Anti-BMN 111 immunogenicity ⁿ		X				X			X		X		X	X	X
PD BMN 111 activity biomarkers ^o	X	X				X	X		X	X	X	X	X		X
NTproCNP (plasma)	X								X	X		X	X		X
ANP (plasma)		X				X			X			X			
cGMP (urine)		X				X	X		X	X	X	X	X		
PD bone and collagen biomarkers ^p	X	X				X	X	X	X	X	X	X	X		X
BSAP (serum)	X	X				X	X		X	X	X	X	X		X
P1NP (serum)	X	X					X		X	X	X	X	X		X
CTX-II (urine)	X	X					X	X	X	X	X	X	X		X
Osteocalcin (serum)	X												X		X
PK ^q		X				X			X		X		X		
Quantitative computed tomography (QCT) of forearm and tibia ^{s,v}	X												X		

Procedure ^a	Screening Day -30 to Day -1	Day 1	Day 2	Day 3	Day 4	Day 10 ± 1 Day	Day 15 ± 1 Day	Day 22 ±1 Day	Day 29 ±1 Day	Day 43 ±7 Days	Day 85 ± 7 Days	Day 127 ±7 Days	Day 183±7 Days M6	Safety Follow-up Day 208 ±7 Days	Early Term
Bone age x-ray (PA of hand and wrist) ^{t,v}	X												X		X ^q
AP lower extremity x-ray ^{u,v}	X												X		X
Lateral lumbar spine x-ray ^w	X												X		
AP x-ray of spine ^x	X														
Concomitant medications ^y	X	X	X	X	X	X	X	X	X	X	X	X	X	X	X
Study drug administration		X	X	X	X	X	X	X	X	X	X	X	X		
Study drug accountability		X	X	X	X	X	X	X	X	X	X	X	X		X
Adverse events ^{aa}	X	X	X	X	X	X	X	X	X	X	X	X	X	X	X
Weekly phone calls or home health visits ^{bb}	Only required on weeks when there are no study visits.														

BOMARIN[®]	BMN 111-202 Amendment 4	Page 42
----------------------------	-------------------------	---------

Table 9.1.2: Optional, Open-label Extension Phase of the Study

Procedure ^a	M8 ± 7 Days	M10 ± 7 Days	M12 ± 7 Days	M15 ± 14 Days	M18 ± 14 Days	M21 ± 14 Days	M24/Study Completion Visit ² ± 14 Days	Safety Follow-up ^{aa} M25 ± 7 Days	Early Term
Physical examination ^e	X	X	X	X	X	X	X	X	X
Tanner Stage of Pubertal Development			X		X		X		X
Pregnancy test ^e	X	X	X	X	X	X	X	X	X
Vital signs ^f	X	X	X	X	X	X	X	X	X
Anthropometric measurements ^g	X	X	X	X	X	X	X	X	X
Weight	X	X	X	X	X	X	X	X	X
Elbow joint range of motion ^h	X	X	X	X	X	X	X	X	X
Hip monitoring (refer to guidance) ^j			X		X		X		X
Sleep apnea assessments ^k			X				X		X ^l
ECG	X	X	X	X	X	X	X		X
ECHO			X		X		X		X
Clinical labs (hematology, chemistry, and urinalysis) ^l	X	X	X	X	X	X	X	X	X
Thyroid function tests							X		
Urine chemistry ^m	X	X	X	X	X	X	X	X	X
Vitamin D							X		X
Anti-BMN 111 immunogenicity ⁿ	X	X	X	X	X	X	X	X	X
PD BMN 111 activity biomarkers ^o			X		X		X		X
NTproCNP (plasma)			X				X		X
ANP (plasma)			X				X		

	BMN 111-202 Amendment 4	Page 43
---	-------------------------	---------

Procedure ^a	M8 ± 7 Days	M10 ± 7 Days	M12 ± 7 Days	M15 ± 14 Days	M18 ± 14 Days	M21 ± 14 Days	M24/Study Completion Visit ^z ± 14 Days	Safety Follow-up ^{aa} M25 ± 7 Days	Early Term
cGMP (urine)			X		X		X		
PD bone and collagen biomarkers ^p	X	X	X	X	X	X	X		X
BSAP (serum)	X	X	X	X	X	X	X		X
P1NP (serum)	X	X	X	X	X	X	X		X
CTX-II (urine)	X	X	X	X	X	X	X		X
Osteocalcin (serum)			X				X		X
PK ^{q,r}	X	X	X	X	X	X	X		
Quantitative computed tomography (QCT) of forearm and tibia ^{s,v}			X				X		X
Bone age x-ray (PA of hand and wrist) ^{t,v}			X		X		X		X
AP lower extremity xray ^{u,v}			X				X		X
Lateral lumbar spine x-ray ^w							X		X
AP x-ray of spine ^x							X		X ^z
Concomitant medications ^y	X	X	X	X	X	X	X	X	X
Study drug administration	X	X	X	X	X	X	X		
Study drug accountability	X	X	X	X	X	X	X		X
Adverse events ^{aa}	X	X	X	X	X	X	X	X	X
Phone calls ^{bb}	Every two weeks (± 3 days) for the first 6 months and every month (± 5 days) for the remainder of the study.								

NOTE: ALL ASSESSMENTS PRE-DOSE EXCEPT WHEN SPECIFIED.

^a Day 10-29 visits have a ± 1-day window; Days 43-183 visits have a ±7 Day window; there is no Day 0. Months 8-12 have a ± 7-day window. Months 15-24 have a ± 14-day window. Measurement and imaging assessments can be conducted either pre-dose or post-dose.

BOMARIN[®]	BMN 111-202 Amendment 4	Page 44
----------------------------	-------------------------	---------

- ^b Medical history, including growth history and ACH-related history, should elicit all major illnesses, diagnoses, and surgeries that the subject has ever had; any prior or existing medical conditions that might interfere with study participation or safety.
- ^c Standing height of the participant’s biological parents will be assessed. Prior to the measurement being taken, each parent is required to complete an ICF specific to parent height assessment. The ICF will be signed prior to the assessment, which can be done at any point in the study. If biological parent is not available during the course of the study to take their standing height, if consented, can provide their stated height.
- ^d If subjects had previous genetic testing, subjects must have either a written letter by the physician confirming genetic testing, including the specific mutation required for the 111-202 study include the identification of FGFR3 mutation (G346E, G375C, G380R, or “other”) OR a lab certification with the study specific mutation documented.
- ^e Complete physical exam includes all major body systems, including assessment of general appearance; CV; dermatologic; head, eyes, ears, nose, and throat; lymphatic; respiratory; gastrointestinal (GI); musculoskeletal; and neurological/psychological and genitourinary. Pregnancy test will be conducted at each indicated visit for female subjects who have begun menses or are 10 years of age and older. Either urine or serum test may be used to confirm pregnancy.
- ^f All treatment visits have pre-dose vital sign assessments. Vital signs at pre-dose include: body temperature in degrees Celsius (°C), heart rate, BP, and respiratory rate. Post-dose measurements include heart rate and BP.

Vital Sign Assessment Frequency				
Screening	After at least 5 min of rest, subject’s BP is taken in sitting position. Then the subject will stand and BP will be taken again at approximately 1 and 3 minutes after standing.			
	Assessment Frequency			
Dosing Visits	0-1 hr post-dose	0-2 hr post-dose	2-4 hr post dose	4-8 hr post-dose
Days 1, 2		q 15 min (± 5 min)	q 30 min (± 5 min)	q 60 min (± 10 min)
Days 3, 4 and dose adjustment visit in optional, open-label extension phase		q 15 min (± 5 min)	q 30 min (± 5 min)	
All other dosing visits	q 15 min (± 5 min); final assessment prior to end of visit (if longer than 1 hr)			

 1. Vital sign measurements are taken once per timepoint in a sitting position after at least 5 minutes of rest. 2. Left brachial arm should be the first method of assessment considered, and the same site should be used for measurement of BP in each subject throughout the study. 3. Heart rate should be taken at each timepoint that BP is measured. 4. When blood samples and BP assessments are scheduled at the same time or within the same time window, BP should be measured before blood samples are drawn. 5. If a BP measurement must be taken after a blood draw, ensure adequate analgesia for the blood draw and wait several minutes before measuring BP. 6. Vital signs may be monitored more frequently or for longer duration post-dose as clinically indicated. 7. If a subject has a hypotensive event (or symptoms potentially consistent with hypotension) or a decrease in systolic BP of 20 mm Hg or more from pre-dose systolic BP, blood pressure and heart rate (BP/HR) should be measured and recorded approximately every 15 minutes for the first hour and every 30 minutes thereafter until the systolic BP returns to pre-dose systolic BP (or within the normal range for this patient as defined by PI) and symptoms (if present) resolve. 				

BOMARIN [®]	BMN 111-202 Amendment 4	Page 45
----------------------	-------------------------	---------

- ^g Growth measures may be collected approximately the same time each day (± 2 hr around the time when the first measurement assessment was taken at Screening). Measurements may include but are not limited to standing height, sitting height, weight, head circumference, upper and lower arm and leg, hand and foot. Measurements not taken in the midsagittal plane should be taken on the right side of the body when possible. Take anthropometric measurements at early termination visit only if subject discontinues after Day 43.
- ^h The same elbow will be used each time the measurement is taken.
- ⁱ If subject is already enrolled, baseline hip assessment, including x-ray of pelvis, will be conducted at next scheduled visit. If this visit overlaps with a scheduled hip-monitoring visit, the hip assessment will be conducted.
- ^j Hip monitoring: this assessment will include medical history of the hip and physical exam to determine changes in hip function or pain with hip range of motion. Changes from baseline will trigger further evaluation.
- ^k If sleep apnea reading is not accurate, subject may need to repeat assessment. Sleep apnea assessment at early termination visit only if subject discontinues after 18 months.
- ^l Clinical labs (hematology, chemistry, and urinalysis) are all pre-dose draws (samples can be drawn anytime during the visit if there is no drug administration).
- ^m First void upon arrival at the clinic. Screening, Days 1, 10, 15, 22, 29, 43, 85, 127, 183, M8, M10, M12, M15, M18, M21, M24, follow-up 4 wk post-escalation dose, safety follow-up, and early termination. One hr, 2 hr, and 4 hr post-dose collected Days 1, 10, 15, 29, 43, 85, 127, 183, M12, M18, M24 (± 20 minutes for all urine sample time points).
- ⁿ Antibodies: Total and neutralizing anti-BMN 111 immunogenicity samples (serum) will be drawn pre-dose at each time point listed on the SOE. Total immunoglobulin E (IgE) and drug-specific IgE will be drawn on Day 1 and in the event of significant hypersensitivity adverse event (as defined in Section 9.10.4.4.6.2), or at Investigator or Sponsor discretion. The drug-specific IgE sample should be drawn at least 8 hr after the event start time and before the next dose. A sample for total IgE and serum tryptase should be drawn within an hour of the start of the event when possible or during the unscheduled safety visit.
- ^o NTproCNP: Screening; at dosing visits, plasma pre-dose and 4 hr post-dose (± 30 minutes); ANP: plasma pre-dose, 15 min post-dose (± 5 minutes), and 2 hr post-dose (± 15 minutes); cGMP: urine pre-dose, 1 hr post-dose, 2 hr post-dose, and 4 hr post-dose (± 20 minutes for all urine sample time points).
- ^p All bone and collagen biomarkers are drawn pre-dose (samples can be drawn anytime during the visit if there is no drug administration).
- ^q For subjects in the 6-month initial phase, on Days 1, 10, 29, 85, and 183, PK samples are collected pre-dose and at 5 (± 2 min), 15 (± 2 min), 30 (± 5 min), 60 (± 5 min), 90 (± 5 min), 120 (± 5 min), and 180 (± 5 min) minutes post dose. For subjects on a fixed dose in the optional, open-label extension phase, full PK samples will be taken at Months 12 and 24. Partial PK samples will be taken at four time points (pre-dose, 15, 30, and 60 minutes post dose) to estimate exposure and to correspond with immunogenicity assessments. These partial PK draws will take place at Months 8, 10, 15, 18, and 21 with immunogenicity assessments (samples can be drawn anytime during the visit if there is no drug administration).
- ^r For subjects whose doses are adjusted upward in the optional, open-label extension phase, full PK samples will be drawn on Day 1 of dose adjustment and at subsequent visits per collection schedule in Table 9.10.2.1.1. Partial PK samples will also be drawn at subsequent visits per collection schedule in Table 9.10.2.1.1.

	BMN 111-202 Amendment 4	Page 46
---	-------------------------	---------

- ^s For measurement of growth plate, BMD, bone length. This scan will be acquired with a standard CT scanner, calibration phantom, and designated software, using a predetermined low radiation dose protocol, which avoids direct radiation to the head and torso.
- ^t Bone age x-ray and AP lower extremity (in the initial phase of the study) are obtained at the early termination visit only if subject discontinues after Day 60 (to reduce unnecessary radiation exposure).
- ^u For AP lower extremity x-ray, assess the same side of the body throughout the study.
- ^v QCT, bone age, and lower extremity (in the optional, open-label extension phase of the study) are obtained at the early termination visit only if the previous assessment was done more than 60 days prior to early termination (unless additional study is recommended by Investigator, BioMarin, or DMC).
- ^w Lateral lumbar spine x-ray at early termination visit only if subject discontinues after 18 months.
- ^x AP x-ray of spine at early termination visit only if subject discontinues after 18 months.
- ^y All medications (prescription, over-the-counter and herbal) and nutritional supplements taken 30 days prior to Screening and throughout the study should be documented.
- ^z Subjects who participate in the open-label extension phase of study 111-202 will have the option to enroll in the long-term extension study 111-205 at the M24/Study Completion Visit. Month 24 assessments will serve as Baseline/screening assessments for entry to study 111-205.
- ^{aa} After written informed consent but before study treatment initiation, only SAEs associated with protocol-imposed interventions will be recorded. After study drug initiation, all AEs and SAEs will be recorded until 4 weeks after either the last administration of study drug or the Early Termination visit. If a subject is discontinued from the study prematurely, AEs and SAEs will be recorded at the Early Termination visit. The Day 208 Safety Follow-up visit is not required if a subject enrolls in the optional, open-label extension study at the Day 183/Month 6 visit. The Month 25 Safety Follow-up visit will be waived if a subject enrolls in the 111-205 extension study at the Month 24/Study Completion visit.
- ^{bb} In the initial phase of the study, on weeks when caregivers/subjects will not see either a home healthcare professional or a study staff member, a phone call by the study staff member to the caregiver/subject will be required. During the call study staff will ask the caregiver about correct administration procedures, assess adverse events (AEs), record concomitant medications, and answer questions. During the optional, open-label extension phase, the call frequency will change to every 2 weeks (\pm 3 days) for the first 6 months of the extension phase and monthly (\pm 5 days) thereafter.

Table 9.1.3: Criteria for Dose Adjustment Visits

Dose Adjustment Recommendation*	Dose Adjustment Made	Dose Adjustment Visit Procedures	Follow-up Phone call	4-week Follow-up Visit (± 2 weeks)	Procedures Done at Follow-up Visit
Next scheduled visit is ≤4 weeks away	At next scheduled visit	The procedures below are done at dose adjustment visits. If the dose adjustment visit happens at a regularly scheduled visit, conduct the remaining scheduled visit procedures as well.	7-10 days post dose adjustment	Schedule 4 weeks after the dose adjustment visit if a regularly scheduled visit does not occur within the visit window	The procedures below are done at adjustment follow-up visits. If the adjustment follow-up visit happens at a regularly scheduled visit, conduct the remaining scheduled visit procedures as well.
Next scheduled visit is >4 weeks away	Unscheduled dose adjustment visit to be done within 4 weeks from DMC decision to dose adjust	
 • Physical exam • Vital signs • Weight • Anthropometry • ECG • Clinical labs • Urine chemistry • Full PK • Concomitant medications • Drug administration • Drug accountability • AEs 			
 • Physical exam • Vital signs • Weight • Clinical labs • ECG • Concomitant medications • Drug administration • Drug accountability • AEs

* If a dose is de-escalated, study staff will request that the subject come in as soon as possible. Follow-up occurs 4 weeks later.

BOMARIN [®]	BMN 111-202 Amendment 4	Page 48
-----------------------------	-------------------------	---------

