13.5 Determination of Sample Size

Approximately 36 pediatric subjects with ACH will participate in this study. No formal sample size calculations were performed.

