13.7 Changes in the Conduct of the Study or Planned Analyses

Only BioMarin may modify the protocol. Any change in study conduct considered necessary by the Investigator will be made only after consultation with BioMarin, who will then issue a formal protocol amendment to implement the change. The only exception is when an Investigator considers that a subject's safety is compromised without immediate action. In these circumstances, immediate approval of the chairman of the IRB/EC must be sought, and the Investigator should inform BioMarin and the full IRB/EC within 2 working days after the emergency occurs.

With the exception of minor administrative or typographical changes, the IRB/EC must review and approve all protocol amendments. Protocol amendments that have an impact on subject risk or the study objectives, or require revision of the ICF, must receive approval from the IRB/EC prior to their implementation.

When a protocol amendment substantially alters the study design or the potential risks or burden to subjects, the ICF will be amended and approved by BioMarin and the IRB/EC, and all active subjects must again provide informed consent.

Note: If discrepancies exist between the text of the statistical analysis as planned in the protocol, and the final SAP, a protocol amendment will not be issued and the SAP will prevail.

 B:OMARIN®	BMN 111-202 Amendment 4	Page 107
---	-------------------------	----------

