3.3 Study Day Derivation

A study day will be obtained by subtracting the initial study drug start date from a visit date plus 1, if the visit date occurs after the initial study drug start date. Otherwise, the study day will be the visit date minus

the initial study drug start date. Therefore, Study Day 1 will be the same date as the initial study drug start date.

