3.4 Visit Windows for Analysis

An assessment for a subject will be classified according to the study day of the assessment where it falls within a window. The analysis windows are designated for each scheduled visit and centered on a target day. If there are two or more assessments within a designated window, the assessment that is closest to the target day will be used for analyses. If the two closest assessments to the target day are equidistant from the target day, the assessments taken on a scheduled visit per CRF page will be used.

Data in BMN111-901 for subjects who enrolled in BMN111-202 study and are included in the corresponding analysis population will be used in efficacy summary tables and figures. The analysis visits and windows for assessments in BMN111-901 are defined below in [Table 3.4.1](#). The analysis windows for assessments in BMN111-202 are defined below in [Table 3.4.2](#) for the initial 6-month period and the extension period. Unless otherwise specified, all analysis are based on derived visits.

Table 3.4.1: Visit Time Windows for Observed Assessments in BMN111-901

Derived Visit	Target Day ^a	Window ^a	
-6M	-183	-228	-138
-12M	-364	-409	-319

^aTarget days and window are relative to the Screening date from the Anthropometric CRF form in BMN111-202

Table 3.4.2: Visit Time Windows for Observed Assessments in BMN111-202

Derived Visit	Target Day ^a	Window
Initial 6-Month Period		
Baseline		The last assessment on or prior to the first dose unless otherwise specified.
Day 1	Day 1	Day 1
Day 2	Day 2	Day 2
Day 3	Day 3	Day 3
Day 4	Day 4	Day 4 – Day 7
Day 10	Day 10	Day 8 – Day 12
Day 15	Day 15	Day 13 – Day 18
Day 22	Day 22	Day 19 – Day 25
Day 29	Day 29	Day 26 – Day 36
Day 43	Day 43	Day 37 – Day 64
Day 85	Day 85	Day 65 – Day 106
Day 127	Day 127	Day 107 – Day 155
Day 183	Day 183	Day 156 – The last date of the Day 183 visit or Day 190 for subjects not entering the extension period
Extension Period (For subjects who enter extension)		
Month 8	Day 243	Day 183 Visit Date + 1 – Day 273
Month 10	Day 303	Day 274 – Day 333
Month 12	Day 364	Day 334 – Day 410
Month 15	Day 456	Day 411 – Day 501
Month 18	Day 547	Day 502 – Day 592
Month 21	Day 638	Day 593 – Day 684
Month 24	Day 730	Day 685 – the actual date of the nominal month 24 visit regardless of the analysis day

^a Target days are relative to the first dosing day.

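### A Day 43 visit held on Day 36 is on time under the protocol, but SAP Table 3.4.2 puts Day 36 in the Day 29 window, so the visit drops out of the Day 43 by-visit summaries.

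*Protocol*

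**What the plan says.** **Protocol.** Footnote a to Tables 9.1.1 and 9.1.2 states "Days 43-183 visits have a ±7 Day window". Section 11.2.8 gives the same ±7 days for Day 43, and Section 11.2.7 gives ±1 day for Day 29.

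**SAP Section 3.4.** Table 3.4.2 sets the Day 29 window at Days 26 to 36 and the Day 43 window at Days 37 to 64. Three rules govern its use:

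- Allocation: "An assessment for a subject will be classified according to the study day of the assessment where it falls within a window".
- Several assessments in one window: "the assessment that is closest to the target day will be used for analyses".
- Scope: "Unless otherwise specified, all analysis are based on derived visits".

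A tie-break in favour of the scheduled CRF visit exists, but its condition is "If the two closest assessments to the target day are equidistant from the target day". The Day 183 and Month 24 rows refer to the actual visit date; the Day 43 row does not.

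**Common ground.** SAP Section 3.3 fixes the day count ("Study Day 1 will be the same date as the initial study drug start date"), and Table 3.4.2 takes its targets relative to the first dosing day. Protocol Section 13.7 settles any conflict over analysis: "a protocol amendment will not be issued and the SAP will prevail".

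**The concern.** Analysis windows are meant to place each scheduled visit under its own label. If a permitted visit day lies outside the visit's own window and inside a neighbour's, an on-schedule assessment is allocated to the wrong visit through no fault of the site. The neighbouring visit then either displaces the value or lends it its label.

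What is at stake is the Day 43 row of the descriptive by-visit tables: laboratory tests, vital signs, biomarkers, growth measures and elbow range of motion. With 8 to 10 children per cohort, one missing child is 1/10 = 10% to 1/8 = 12.5% of a cohort's Day 43 cell.

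**Working it through.** **1. Permitted days against analysis windows.** The permitted range is target ± protocol window. For the monthly visits the SAP's target days are used, since the protocol names months only.

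| Visit | Permitted days | SAP window | Permitted days outside |
|---|---|---|---|
| Day 10 | 9–11 | 8–12 | none |
| Day 15 | 14–16 | 13–18 | none |
| Day 22 | 21–23 | 19–25 | none |
| Day 29 | 28–30 | 26–36 | none |
| **Day 43** | **36–50** | **37–64** | **Day 36** |
| Day 85 | 78–92 | 65–106 | none |
| Day 127 | 120–134 | 107–155 | none |
| Day 183 | 176–190 | 156 to visit date, or Day 190 | none |
| Month 8 | 236–250 | day after Day 183 visit to 273 | none |
| Month 10 | 296–310 | 274–333 | none |
| Month 12 | 357–371 | 334–410 | none |
| Month 15 | 442–470 | 411–501 | none |
| Month 18 | 533–561 | 502–592 | none |
| Month 21 | 624–652 | 593–684 | none |
| Month 24 | 716–744 | 685 to visit date | none |

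The only mismatch is 43 − 7 = 36, which lies in 26–36.

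**2. What happens to a Day 36 assessment.** Its distance from the Day 29 target is 36 − 29 = 7 days. An on-time Day 29 visit (Days 28, 29 or 30) is 1, 0 or 1 day away. There is no tie, so the tie-break does not apply. Under Table 9.1.1:

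- *Scheduled at both visits* (vital signs, weight, clinical laboratory tests, urine chemistry, NT-proCNP, cGMP, BSAP, P1NP, CTX-II): the Day 29 value is used and the Day 36 value is not.
- *Scheduled at Day 43 but not Day 29* (anthropometry, elbow range of motion): the Day 36 value is the only one in the window and takes derived visit Day 29.

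Either way the child has no Day 43 value unless another assessment falls on Days 37 to 64.

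**3. Why Day 36 and no other boundary.** Where the midpoint between two adjacent fixed targets is a whole day, the table always gives that day to the earlier visit: Days 7, 36, 64, 106, 155, 273, 410 and 684. From step 1, Day 36 is the only one of the eight on which the protocol permits a scheduled visit.

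**4. Size.** The documents give no visit-date distribution, so the share of visits on Day 36 is an assumption (36 children, all attending, independent timing):

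| Assumed share on Day 36 | Expected children | Chance of at least one |
|---|---|---|
| 0 | 0 | 0 |
| 1% (illustrative) | 36 × 0.01 = 0.36 | 1 − 0.99^36 = 0.30 |
| 1/15 = 6.7% (uniform) | 36/15 = 2.4 | 1 − (14/15)^36 = 0.92 |

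**The case against.** **The table follows one consistent rule.** It gives equidistant days to the earlier visit throughout. Operational and analysis windows serve different purposes, nothing in the documents requires one to contain the other, and the SAP prevails. This is fair as a description. The convention, however, is harmless at the other seven midpoints, where no scheduled visit is permitted, and it misplaces an on-schedule visit only at Day 36.

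**A reader might infer that the data are discarded. The documents do not support that.** The value is missing only from the derived-visit summary. Laboratory shift tables take the most extreme post-baseline result from scheduled and unscheduled visits (SAP 14.2). Laboratory and vital sign results are also listed (Protocol 13.4).

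**A reader might also infer that the growth results are compromised.** They are not. Annualized growth velocity is summarised at six-month points (SAP 12.2.1), and the exploratory tests are at Months 6, 12, 18 and 24 (SAP 12). Adverse events are attributed by start date (SAP 14), not by visit window.

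**A Day 29 row for anthropometry is not certain to appear.** The SAP summarises growth measures at scheduled assessments and does not say whether it would print a row for a visit at which they are not scheduled. The derived label follows from the rule; its appearance in a table is an inference.

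**Some windowing text cannot be seen.** The SAP's change summary mentions a windowing clarification for two subjects, with details redacted. Whether it concerns Day 36 cannot be judged.

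**Conclusion.** The mismatch is real and follows from the two documents' own numbers. A Day 43 visit on Day 36 complies with the protocol, yet the SAP rules visible here leave it out of the Day 43 by-visit summaries. It is the only such case among the scheduled visits checked.

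The point is minor. It touches 1 of 15 permitted days and one intermediate descriptive time point. The number of children affected is unknown and may be zero. The figures of 2.4 children and a 92% chance of at least one hold only under uniform timing, for which the documents give no support; if visits cluster on Day 43, both fall. They should be read as the result of one assumption, not as an estimate.

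**What to change.** In SAP Table 3.4.2, set Day 29 to Days 26–35 and Day 43 to Days 36–64, and carry the change into the programming specification. On-time Day 29 visits (28–30) stay in 26–35, and all 15 permitted Day 43 days (36–50) fall in 36–64. Day 36 is 36 − 29 = 43 − 36 = 7 days from each target, so closeness is not compromised.

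The cost is two numbers and one disclosed exception to the table's practice of giving equidistant days to the earlier visit. A Day 29 visit held as late as Day 36 would then be classed as Day 43, but such a visit is already outside its ±1-day protocol window. Classifying scheduled visits by their nominal label when they fall within the protocol window would also close the gap, but changes more of the SAP's rule.

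Either way, count the Day 43 visits held on Day 36. If there are none, the change has no effect on the Day 43 visits.
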